5.4.3 Reporting Requirements for Pregnancies

5.4.3.1 Pregnancies in Female Patients

Female patients of childbearing potential will be instructed to immediately inform the investigator if they become pregnant during the study or within 28 days after the last dose of study drug. A Clinical Trial Pregnancy Reporting Form should be completed and submitted to the Sponsor or its designee immediately (i.e., no more than 24 hours after learning of the pregnancy), either by faxing or by scanning and emailing the form using the fax number or email address provided to investigators. Pregnancy should not be recorded on the Adverse Event eCRF. The investigator should discontinue study drug and counsel the patient, discussing the risks of the pregnancy and the possible effects on the fetus. Monitoring of the patient should continue until conclusion of the pregnancy. Any serious adverse events associated with the pregnancy (e.g., an event in the fetus, an event in the mother during or after the pregnancy, or a congenital anomaly/birth defect in the child) should be reported on the Adverse Event eCRF. In addition, the investigator will submit a Clinical Trial Pregnancy Reporting Form when updated information on the course and outcome of the pregnancy becomes available.

5.4.3.2 Pregnancies in Female Partners of Male Patients

Male patients will be instructed through the Informed Consent Form to immediately inform the investigator if their partner becomes pregnant during the study or within 28 days after the last dose of study drug. A Clinical Trial Pregnancy Reporting Form should be completed and submitted to the Sponsor or its designee immediately (i.e., no more than 24 hours after learning of the pregnancy), either by faxing or by scanning and emailing the form using the fax number or email address provided to investigators. Attempts should be made to collect and report details of the course and outcome of any pregnancy in the partner of a male patient exposed to study drug. The pregnant partner will need to sign an Authorization for Use and Disclosure of Pregnancy Health Information to allow for follow-up on her pregnancy. After the authorization has been signed, the investigator will submit a Clinical Trial Pregnancy Reporting Form when updated information on the course and outcome of the pregnancy becomes available. An investigator who is contacted by the male patient or his pregnant partner may provide information on the risks of the pregnancy and the possible effects on the fetus, to support an informed decision in cooperation with the treating physician and/or obstetrician.

5.4.3.3 Abortions

Any abortion should be classified as a serious adverse event (as the Sponsor considers abortions to be medically significant), recorded on the Adverse Event eCRF, and

Pirfenidone—F. Hoffmann-La Roche Ltd

reported to the Sponsor immediately (i.e., no more than 24 hours after learning of the event; see [Section 5.4.2](#)).

5.4.3.4 Congenital Anomalies/Birth Defects

Any congenital anomaly/birth defect in a child born to a female patient exposed to study drug or the female partner of a male patient exposed to study drug should be classified as a serious adverse event, recorded on the Adverse Event eCRF, and reported to the Sponsor immediately (i.e., no more than 24 hours after learning of the event; see [Section 5.4.2](#)).

5.5 FOLLOW-UP OF PATIENTS AFTER ADVERSE EVENTS

5.5.1 Investigator Follow-Up

The investigator should follow each adverse event until the event has resolved to baseline grade or better, *or* the event is assessed as stable by the investigator, the patient is lost to follow-up, or the patient withdraws consent. Every effort should be made to follow all serious adverse events considered to be related to study drug or trial-related procedures until a final outcome can be reported.

During the study period, resolution of adverse events (with dates) should be documented on the Adverse Event eCRF and in the patient's medical record to facilitate source data verification.

All pregnancies reported during the study should be followed until pregnancy outcome.

5.5.2 Sponsor Follow-Up

For serious adverse events, adverse events of special interest, and pregnancies, the Sponsor or a designee may follow up by telephone, fax, electronic mail, and/or a monitoring visit to obtain additional case details and outcome information (e.g., from hospital discharge summaries, consultant reports, autopsy reports) in order to perform an independent medical assessment of the reported case.

5.6 ADVERSE EVENTS THAT OCCUR AFTER THE ADVERSE EVENT REPORTING PERIOD

The Sponsor should be notified if the investigator becomes aware of any serious adverse event that occurs after the end of the adverse event reporting period (defined as 28 days after the last dose of study drug), if the event is believed to be related to prior study drug treatment. These events should be reported through use of the Adverse Event eCRF. However, if the EDC system is not available, the investigator should report these events directly to the Sponsor or its designee, either by faxing or by scanning and

Pirfenidone—F. Hoffmann-La Roche Ltd

emailing the Serious Adverse Event/Adverse Event of Special Interest Reporting Form using the fax number or email address provided to investigators.

5.7 EXPEDITED REPORTING TO HEALTH AUTHORITIES, INVESTIGATORS, INSTITUTIONAL REVIEW BOARDS, AND ETHICS COMMITTEES

The Sponsor will promptly evaluate all serious adverse events and adverse events of special interest against cumulative product experience to identify and expeditiously communicate possible new safety findings to investigators, IRBs, ECs, and applicable health authorities based on applicable legislation.

To determine reporting requirements for single adverse event cases, the Sponsor will assess the expectedness of these events using the following reference documents:

- Pirfenidone *Local Instruction for Use*
- Pirfenidone Core Data Sheet

The Sponsor will compare the severity of each event and the cumulative event frequency reported for the study with the severity and frequency reported in the applicable reference document.

Reporting requirements will also be based on the investigator's assessment of causality and seriousness, with allowance for upgrading by the Sponsor as needed.

Additionally, the IDMC will conduct regular review of the trial safety data, as described in [Section 5.2.3.2](#).

6. STATISTICAL CONSIDERATIONS AND ANALYSIS PLAN

Data handling will be the responsibility of Data Matrix. The data will be inspected for inconsistencies by performing validation checks. Any inconsistencies found will be resolved by the monitor after contacting the Investigator. When the data in the database are considered clean and the subjects allocated to subject samples in a data review, the database will be locked to prevent unauthorized access. Next, the database will be made available as SAS® files for statistical analysis.

All details regarding the statistical analysis and the preparation of tables, listings and figures will be described in the Statistical Analysis Plan prepared by Data Matrix and approved by F. Hoffmann-La Roche Ltd. before database lock.

The statistical analysis will be performed by Data Matrix.

Pirfenidone—F. Hoffmann-La Roche Ltd

The main subject samples of interest are defined as follows.

The 'Allocated to treatment' set will consist of all subjects who:

- Gave their Informed Consent and
- Has successfully completed Screening procedures.

The 'Treated set' (TS) will consist of all subjects who:

- Were in the 'Allocated to treatment' set and
- Received any dose of the study treatment.

The 'Full analysis' set (FAS) will consist of all subjects who:

- Were included in the 'Treated' set and
- Had data for at least one post-baseline assessment of any efficacy measurement.

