6.2. Analysis Populations

The main patient samples of interest are defined as follows.

The ‘All enrolled patients’ set will consist of all patients who:

Gave their Informed Consent.

The ‘Allocated to treatment’ set will consist of all patients who:

Gave their Informed Consent and

Had successfully completed Screening procedures.

The ‘Treated set’ (TS) will consist of all patients who:

Were in the ‘Allocated to treatment’ set and

Received any dose of the study treatment.

The ‘Full analysis’ set (FAS) will consist of all patients who:

- Were included in the ‘Treated’ set and
- Had data for at least one post-baseline assessment of any efficacy measurement.

The ‘Complete case set’ (CCS) will include FAS patients who

- Provided FVC data at 26-week assessment.

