7.2. Protocol Deviations⁶

Number and percentage of patients with at least one protocol deviation will be tabulated (Allocated to treatment set). All protocol deviations will be listed (All Enrolled patients).

⁶ This section is based on the section 9.2 “Protocol deviations” of clinical study Protocol.

ML39355_STATISTICAL ANALYSIS PLAN_Final 2.0_17 June 2020

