All Enrolled patients

Page X of X

	Total (N = XX) n (%)
Patients who signed the Informed Consent Form	XX
Screening Failures	XX
Reasons for premature discontinuation	XX
Patient request or withdrawal of consent	XX
Presence or development of Inclusion/Exclusion criterion (-a)	XX
Allocated to treatment	xx
Treated during the treatment period	XX (XX.X)
Patients continuing (treated) in the rollover study	XX (XX.X)
Completed	XX (XX.X)
Terminated Prematurely	XX (XX.X)
Reasons for premature discontinuation	
Pregnancy	XX (XX.X)
Unacceptable tolerability and personal safety profile (e.g. adverse events listed in Section 5.1.2 of Protocol, or serious adverse events related to study treatment)	XX (XX.X)
Patient request or withdrawal of consent	XX (XX.X)
Any medical condition that the investigator or Sponsor determines may jeopardize the patient's safety if he or she continues in the study	XX (XX.X)
Investigator or Sponsor determines it is in the best interest of the patient for other reasons	XX (XX.X)
Protocol deviation (at Sponsor's discretion) (e.g. refusal to follow study requirements)	XX (XX.X)
Termination of the whole study by the Sponsor	XX (XX.X)
Lung transplantation	XX (XX.X)
The incidence or severity of adverse events in this or other ongoing studies of pirfenidone indicates a potential health hazard to patients	XX (XX.X)
Patient enrollment is unsatisfactory	XX (XX.X)
Administrative and regulatory reasons	XX (XX.X)
Presence or development of Inclusion/Exclusion criterion (-a)	XX (XX.X)
Other	XX (XX.X)

ML39355_STATISTICAL ANALYSIS PLAN_Final 2.0_17 June 2020

Other reason 1	XX (XX.X)
Other reason 2	XX (XX.X)
...	XX (XX.X)

N: the number of patients who signed the Informed Consent Form.

n: the number of patients within a specific category. Percentages are calculated based on number of patients Allocated to Treatment.

Path to the program code, date and time of output

Data extracted: DD.MM.YYYY

ML39355_STATISTICAL ANALYSIS PLAN_Final 2.0_17 June 2020

F. Hoffmann-La Roche Ltd
ML39355

Table 1.2 Violation of eligibility criteria
Screening Failures
Page X of X

	Total (N = XX)
Patients with any violation of eligibility criteria	XX
Patients with any violation of inclusion criteria	XX
Inclusion criterion #1	XX
Inclusion criterion #2	XX
...	...
Patients with any violation of exclusion criteria	XX
Exclusion criterion #1	XX
Exclusion criterion #2	XX
...	...

N: the number of Screening Failures.

n: the number of patients within a specific category.

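### A dose alone does not place a patient in the Treated set: entry also depends on an undefined screening condition, so a patient dosed in error could drop out of the safety tables (minor)

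*Protocol*

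**What the plan says.** Protocol section 6 builds its analysis sets in a chain. The Allocated to treatment set needs informed consent and "Has successfully completed Screening procedures". The Treated set needs "Were in the 'Allocated to treatment' set and" and "Received any dose of the study treatment". The FAS begins with "Were included in the 'Treated' set and" and adds a post-baseline efficacy value. SAP 6.2 keeps the same gate ("Had successfully completed Screening procedures") and places the Complete case set inside the FAS.

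Protocol 6.5 assigns safety and tolerability analyses to the Treated set. Protocol 6.2 and SAP section 7 count a patient as at risk for adverse events only if in that set. SAP section 8 uses the FAS and CCS for efficacy.

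On deviations, SAP 7.2 says: "Number and percentage of patients with at least one protocol deviation will be tabulated (Allocated to treatment set". The same section lists all deviations for all enrolled patients.

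Neither document says what makes screening successful, and neither has a rule for a patient who is dosed without it.

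**The concern.** A safety population is normally defined by exposure, so that everyone who took the drug is counted whatever their eligibility. Here a second condition sits in front of exposure. There is no separate safety set to catch a patient who fails it, because the Treated set is the safety set.

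The patients at risk of being left out are those dosed in breach of the screening process, and they are of particular safety interest. If such a patient had a serious event or died, the event would be missing from the numerators, the denominators and the deaths table. The exposure that led to it would be missing from the dosing tables and dosing listings.

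A further weakness is timing. Protocol section 6 has patients assigned to the analysis sets at a data review before database lock. In an open-label study outcomes are already visible at that point. An undefined phrase leaves a judgement to be made then, whereas receipt of a dose is a fact.

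**Working it through.** **1. Trace the nesting.** CCS lies within FAS, FAS within the Treated set, and the Treated set within the Allocated set. A patient outside the Allocated set is therefore outside all four, whatever was taken.

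**2. Check which outputs use which set.**

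| Output | Population | Patient dosed but not Allocated |
|---|---|---|
| Safety tables 3.1 to 3.27, including 3.14 Deaths | Treated set | Absent |
| Efficacy tables 2.1 to 2.19 | FAS or CCS | Absent |
| Listings 26 to 28 (drug administration, exposure, overdose) | Treated set | Absent |
| Table 1.5 (deviation count) | Allocated set | Absent |
| Listing 5 (deviations) | All Enrolled | Present |
| Listings 23 to 25 (AEs, exacerbations, SAE/AESI) | All Enrolled | Present |
| Listings 30, 31, 33 (laboratory, ECG) | All Enrolled | Present |

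Listing 23 could therefore show an event with an action taken on study drug for a patient who has no entry in the dosing listings.

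**3. Test the two readings of the gate.**

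- *Procedures done.* A patient with every screening procedure performed but one criterion missed stays in the Treated set. A patient dosed with screening incomplete, or formally recorded as a screen failure, does not.
- *Criteria met.* Both of those patients are lost, and so is any dosed patient who failed a criterion.

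Some dosed patients can be lost under either reading. The readings differ only in how many.

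**4. Sample size.** The plan's own figure reproduces: n = p × q × (z/E)² = 0.601 × 0.399 × (1.96/0.125)² = 58.96, set to 60. Nothing in that calculation depends on this point.

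**5. Illustration of size.** Assume 60 patients are dosed and k of them are not Allocated. The documents give no k; 1 to 3 is chosen only to show scale. Suppose each of the k has a serious event and nobody else does. Intervals are exact (Clopper-Pearson) 95%.

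| k | As written | Upper limit | By exposure | Interval |
|---|---|---|---|---|
| 1 | 0/59 | 6.1% | 1/60 = 1.7% | 0.04% to 8.9% |
| 2 | 0/58 | 6.2% | 2/60 = 3.3% | 0.4% to 11.5% |
| 3 | 0/57 | 6.3% | 3/60 = 5.0% | 1.0% to 13.9% |

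The adverse event shells report n (%) and event counts without intervals, so the intervals are for scale only.

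**6. Primary endpoint.** Death before Week 26 is scored as FVC 0%. Take the plan's cited values of 67.8 at baseline and 65.3 at Week 26, a mean change of −2.5. If one excluded patient had that baseline, died before Week 26 and had a post-baseline efficacy value, the mean over 60 patients would be (59 × (−2.5) + (−67.8))/60 = −215.3/60 = −3.6, against −2.5 with the patient left out.

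**The case against.** A reader might infer that every patient dosed despite failing an eligibility criterion is removed from every safety and efficacy table. The documents do not establish that, for these reasons:

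- **The gate refers to procedures.** Protocol 4.5.13.2 lists screening procedures, while Protocol 4.5.13.3 makes confirmation of eligibility a separate Day 1 item. A patient whose ECG and laboratory tests were done but whose result breached a limit can be read as having completed screening.
- **The shells suggest the inclusive reading.** Treated-set Table 1.12 has rows for positive serology, and Table 1.17 has a row for smoking within 28 days; both match exclusion criteria. Table 1.1 gives "Presence or development of Inclusion/Exclusion criterion (-a" as a discontinuation reason with percentages on the Allocated set. These rows show how the sponsor may apply the phrase; they do not prove that the definition and shells conflict. The Table 1.1 wording also covers a criterion that arises after allocation.
- **Table 1.9 is not evidence.** Its row for a scan inconsistent with UIP records each central reader separately. The second reads only when the first disagrees with the local opinion, so the row can arise in normal review.
- **The case needs a deviation.** Protocol 4.3.2 starts treatment only after successful screening, and central review of HRCT and any biopsy remains in place. The planned 45% screen failure rate says nothing about how many failures would be dosed.
- **The events are not lost.** The All Enrolled listings keep them, and SAE reporting and IDMC review do not depend on set membership.

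All of this stands, and it limits the point in scope and severity. It does not remove it. The phrase remains undefined, a dosed patient with incomplete screening is excluded even on the generous reading, and no rule brings that patient back. Central review also does not cover the ECG and laboratory criteria, which are assessed locally.

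**Conclusion.** The point holds as a minor one. As worded, taking a dose does not qualify a patient for the safety population. A patient dosed with screening incomplete or formally recorded as a screen failure would leave the Treated set, FAS and CCS tables, Listings 26 to 28 and the Table 1.5 count. On a strict reading, so would any dosed patient who failed a criterion.

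The likely number is small and cannot be taken from the documents. Under the illustrative assumption of one such patient among 60 dosed, one serious event moves from 0/59 to 1/60, and one death scored as zero moves the assumed mean change from −2.5 to −3.6. The harm is to the summarised results, since listings and expedited reporting are unaffected.

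**What to change.** In Protocol section 6 and SAP 6.2, define the Treated set as all patients who received at least one dose of study treatment, and delete the condition on the Allocated set. The FAS and CCS then follow without further change. Flag eligibility failures and incomplete screening among dosed patients as protocol deviations. Build Table 1.5 on patients who were allocated or treated. Listings 26 to 28 correct themselves because they already use the Treated set.

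The cost is a line in each set definition and a population change for one table. No extra data and no sample-size change are needed. If no patient is dosed outside the screening process, the results are identical. If one is, the tables may look slightly less favourable.

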6.1 DETERMINATION OF SAMPLE SIZE

Taking into account study design (single group prospective study), sample size was estimated based on feasibility of subject enrollment with precision-based approach. In the ASCEND study primary efficacy endpoint (Percent Predicted FVC) in pirfenidone group changed from 67.8 (11.24) (denoted as mean (SD)) at baseline to 65.3 (14.52) at week 26, with stable disease (decline in FVC < 10 % to 0 %) in 60.1 % of study subjects.

The required sample size for two-sided 95% confidence level can be calculated using the following formula:

$$n = \hat{p}\hat{q} \left(\frac{Z_{\alpha/2}}{E} \right)^2 ;$$
$$n = 0.601 \times 0.399 \left(\frac{1.96}{0.125} \right)^2 \approx 58.96.$$

Assuming previous calculations, 60 subjects included in the study will be sufficient for study parameters estimation. Taking into account study goals and the notion that the study drug is a product for the treatment of an orphan drug, margin of error of 0.125 is considered sufficient for parameter estimation. For precision-based sample size justification, with a sample size of 60 patients, an expected mean value of 2.5% and standard deviation of 20, distance from the mean to limit of the two-sided 95% confidence interval for the mean Change from Baseline to Week 26 (Percent Predicted FVC) will extend about 5 (margin of error). The SD for change from baseline at week 26 is conservatively estimated based on the results of the ASCEND study as standard deviation for Percent Predicted FVC in pirfenidone group at week

Pirfenidone—F. Hoffmann-La Roche Ltd

26 (14.52) multiplied by $\sqrt{2}$ (Machin et al., 1997). This is also in line with the results of CAPACITY programme (Noble et al. 2011) in which the SD of changes from baseline was 17 - 20 at week 72.

Taking into account an expected rate of screening failures about 45%, up to 109 patients will be screened for eligibility.

6.2 SUMMARIES OF CONDUCT OF STUDY

Time-Related Definitions

The baseline period will be defined as the period from Informed Consent to the first study drug administration. The baseline value for a variable in common cases (except efficacy analysis) is defined as the last non-missing value collected before the first study drug administration.

All variables planned to be measured at one or more time points, and supposed to be time-related will be windowed.

Coding Systems

AEs and medical history Investigator terms will be assigned to a lowest level term (LLT) and a preferred term (PT) and will be classified by high level term (HLT) and primary system organ class (SOC) according to the Medical Dictionary for Regulatory Activities (MedDRA) thesaurus.

Prior and concomitant medications will be classified according to active drug substance using the WHO drug dictionary. The generic name, the preferred name and the WHO name will be assigned.

In addition, the Anatomical Therapeutic Chemical (ATC) classes will be assigned to the drug ID. ATC codes are defined to the 4th level. For each medication, the primary ATC class will be assigned manually based on the generic name and the reason for use.

Default Summary Statistics

The default summary statistics for quantitative and ordinal variables will be the number of observations (n), mean, standard deviation (SD), median, minimum (Min) and maximum (Max) for subjects with data. For efficacy data 95% CI will be provided additionally.

Default Frequency Tabulations

For qualitative variables, per category the numbers and frequencies of subjects with non-missing data (n, %) will be the default summary presentation.

Pirfenidone—F. Hoffmann-La Roche Ltd

For AEs and medical history, however, the denominator for the percentage calculation will be the number of subjects at risk. A subject will be considered at risk if the subject is in the *Treated set*.

Subject Listings

Individual subject listings will be produced for all raw data.

Handling missing values

For missing FVC data imputation, patients will be classified into different patterns depending on the availability of data:

Patients with a 26 week FVC value:

1. those who received *study* drug until 26 weeks;
2. those, who prematurely discontinued *study* drug, but who were followed up until Week 26.

Patients without a 26 Week FVC value:

1. those who were alive at 26 weeks;
2. those, who died before 26 weeks.

Missing data at other visits before Week 26 (primary outcome variable) will not be imputed.

The following imputation methods including sensitivity analyses will be applied for patients with pattern 3 - 4:

Assuming that deaths of the patients (pattern 4) is likely to be related to worsening of IPF, these unobserved FVC values should be lower than those in patients who did not die prior to Week 26. Methods for handling missing data due to death will include the following:

- Replacement with the worst possible value (FVC= 0 mL or 0%) (Primary analysis).
- Replacement with worst observed FVC value at week 26 (Sensitivity analysis).

Pirfenidone—F. Hoffmann-La Roche Ltd

136/Protocol ML39355, Version 2 dated 09-Jun-2018

- Replacement with an intermediate value (FVC =1500 mL or 50%) (Sensitivity analysis).

Missing data due to reasons other than death (pattern 3) will be replaced with imputed values based on the average measurements for “similar” patients at that time point (Primary analysis). Similar patients are those without missing data before that time point and whose data have the smallest sum of squared deviations (SSD) from that patient for all visits prior to the one with the missing data. Missing data due to lung transplant will be imputed using the SSD method even if the patient dies after lung transplant. A sensitivity analysis will use the data imputed with last observation carried forward method (LOCF).

Complete case analysis will also be performed as a sensitivity analysis.

